## 1 List of Abbreviations

Abbreviation	Abbreviation definition
TOPPS	Treating Opioid Patients' Pain and Sadness
HE	Health education
BHS	Behavioral Health Specialist
OBAT	Office-based addiction treatment
BHS	Behavioral Health Specialist
RA	Research Assistant
CAM	Complementary and Alternative Medicine
OUD	Opioid Use Disorder
BA	Behavioral Activation
ACT	Acceptance and Commitment Theory
BPI	Brief Pain Inventory
VAS	Visual Analog Scale
PHQ-9	Patient Health Questionnaire-9
BADS	Behavioral Activation for Depression Scale
PASS	Pain Anxiety Symptoms Scale
SOP	Standard Operating Procedure
MSSI	Modified Scale for Suicidal Ideation
SCID	Structured Clinical Interview for DSM
SSTAR	Stanley Street Treatment and Resources
BMC	Boston Medical Center
BU	Boston University
BUP	Buprenorphine
EHR	Electronic Health Records
CDW	Clinical Data Warehouse
MOUD	Medications for Opioid Use Disorder
RW	[name] (PI)
AE	Adverse Event
SAE	Serious Adverse Event
DSMB	Data Safety and Monitoring Board
IRB	Institutional Review Board
CRF	Case Report Form
MICE	Multiple imputation by chained equation
MAR	Missing at random
SEM	Structural Equation Models
ICH	International Council for Harmonization

## 2 Protocol Summary

Title:	Treating Opioid Patients' Pain and Sadness (TOPPS)
Population:	163 participants currently being treated with buprenorphine

Intervention:	Intervention: 12-week lifestyle psychoeducation about pain, depression, and opioid use; as well as values-based, behavioral activation to increase engagement in meaningful activities. Timing: 3-months Method: Randomized controlled trial
Objectives:	1) to determine whether the TOPPS intervention, compared to HE, results in less pain interference and pain severity over the 3-month treatment phase; 2) to determine whether TOPPS, compared to HE, results in less depressive symptoms over 3 months; 3) to determine whether TOPPS, compared to HE, results in sustained improvements in pain interferences, pain severity, depressive symptoms, and buprenorphine treatment retention (self-reported continuous treatment) over the 12 months of the study.
Design/Methodology:	163 participants who are currently being treated with buprenorphine and who endorse pain and depressive symptoms were randomized into the trial. Recruitment occurred from two primary care, office-based addiction treatment (OBAT) buprenorphine clinics, as well as through online advertisement. Following consent and the baseline interview, participants were randomized to one of two study arms: the TOPPS intervention or health education. The TOPPS intervention consists of 3 main components: 1) psychoeducation about pain, depression, opioid use, their interactions, and the role of avoidance; 2) coaching in how to be an informed, activated patient; and 3) values-based, behavioral activation, to increase engagement in meaningful activities. The intervention is a total of 6 phone-based sessions over 12 weeks with a Behavioral Health Specialist (BHS). The control arm (health education) involves six sessions led by the same BHS. The first health education session is titled "What to Eat." Participants then select five additional topics, one for each of the remaining sessions. Topics include, "What Not to Eat," "Colds, Germs, and Flu," "Preventing Cancer," "Diabetes," "Protecting your heart," "Getting a Good Night's Sleep," "Complementary and Alternative Medicine (CAM)," "Caffeine," and "Physical Activity." Follow-up interviews are conducted by trained Research Assistants (RAs) at 1, 2-, 3-, 6-, 9-, and 12-months (for participants enrolled prior to XX) post-enrollment.
Total Study Duration:	5 years
Subject Participation Duration:	9-12 months

### 3 Background/Rationale & Purpose

#### 3.1 Background Information

An estimated 1.7 million adults used prescribed buprenorphine in 2019 [1]. >40% of those individuals have pain that interferes with daily activities and affects buprenorphine treatment outcomes [2].

Approximately 29–48% of individuals with substance use disorder are estimated to have depression [3,4]. Further, depression and pain often co-occur, with estimates of up to 72% of people with chronic pain meeting criteria for depression [5]. Though both pain and depression are common among patients with OUD (Opioid Use Disorder), these conditions often go unaddressed [6]. There are limited non-pharmacological treatments available with the goal of improving pain outcomes. Furthermore, pain can interfere with effectiveness of antidepressants [7,8]. However, addressing pain or depression alone can be ineffective for patients suffering with both [9]. Studies have demonstrated that behavioral interventions are effective in patients with comorbid conditions, including substance use, depression, and chronic pain [10].

This study will be conducted in compliance with the protocol, applicable regulatory requirements, and policies and procedures of the Boston Medical Center and Boston University Medical Campus Human Research Protection Program and of the Institutional Review Board of Boston University Medical Campus

### 3.2 Rationale and Purpose

We sought to develop and study an intervention to address this commonly occurring and often debilitating triad of conditions, pain, depression, and opioid use disorder. The TOPPS (Treating Opioid Use, Persistent Pain, and Sadness) intervention integrates and builds upon existing behavioral therapies for chronic pain and depression. Studies have shown that behavioral activation (BA) and values-based approaches such as Acceptance and Commitment Therapy (ACT) are efficacious treatments for chronic pain and depression [11,12]. Behavioral activation is frequently used in treatments for chronic pain and depression to counteract behavioral avoidance that interferes with daily functioning by increasing engagement with valued and enjoyable life activities [13]. BA therapy and ACT have demonstrated reductions in pain interference, stress, depression, and pain-related anxiety [14,15]. Similar to the ACT model, the TOPPS intervention supports participants in clarification of personal values, long and short-term goal setting and behavioral activation in service of these values, and nonjudgmental acceptance of experiences as they pursue their goals.

We have performed two promising pilot trials addressing pain depression together in vulnerable populations. The first involved persons living with HIV (N = 58) [16]. A more recent randomized trial (N = 21) of TOPPS in persons receiving buprenorphine at two primary care sites showed promising decrements in pain interference with daily activities and pain severity when compared to the Health Education (HE) control condition. We thus planned to further evaluate the effectiveness of TOPPS in a fully powered trial. The TOPPS intervention includes psychoeducation about pain, depression, and opioid use; as well as values-based, behavioral activation to increase engagement in meaningful activities. The main study outcomes are reduced and sustained pain severity, pain interference, depressive systems, and buprenorphine treatment retention.

## 4 Objectives

### 4.1 Study Objectives

The described study is a randomized clinical trial of the Treating Opioid Use, Persistent Pain, and Sadness (TOPPS) intervention compared to health education (HE) contact-control condition among

persons receiving buprenorphine for opioid use disorder. The study objectives are as follows: 1) to determine whether the TOPPS intervention, compared to HE, results in less pain interference and pain severity over the 3-month treatment phase; 2) to determine whether TOPPS, compared to HE, results in less depressive symptoms over 3 months; 3) to determine whether TOPPS, compared to HE, results in sustained improvements in pain interferences, pain severity, depressive symptoms, and buprenorphine treatment retention (self-reported continuous treatment) over the 12 months of the study. Mechanisms by which TOPPS may reduce pain interference will also be examined, including 1) (increased) activities of engagement; 2) (decreased) avoidance of meaningful life activities; and 3) (decreased) fear of pain.

## 4.2 Study Outcome Measures

### 4.2.1 Primary Outcome Measures

The primary aim of this study is to test the hypothesis that participants randomized to the TOPPS intervention, compared to the Health Education condition will 1) have less pain interference and pain severity, as measured by the BPI (Brief Pain Inventory) and a Visual Analog Scale (VAS) at the end of the 3-month treatment phase.

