### 4.2.3 Exploratory Outcome Measures

We will examine potential mediators of change in our primary outcomes during the 3- month treatment period, decreased avoidance of life activities (BADS [Behavioral Activation for Depression Scale]), and decreased pain anxiety or fear of pain (PASS [Pain Anxiety Symptoms Scale]).

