## 15.3 Statistical Methods

We will present descriptive statistics. Random effects logistic regression will be used to determine if treatment condition, demographic characteristics, or baseline outcome measures predict study attrition. Any variables that significantly ( $p < .10$ ) predict study attrition will be included in multiple imputation models and as covariates in multivariate models testing the effects of intervention. Graphical methods will be used to evaluate the distributions of outcome variables, examine model residuals, describe change in outcomes over time, and guide the specification generalized linear mixed models testing intervention effects. A 2-tailed probability of Type I error  $< 0.05$  will be used for all null hypothesis tests. Missing data due to participant attrition and item non-response is inevitable. We will conduct intent-to-treat analysis using multiple imputation by chained equation (MICE) to generate fully populated data sets [20]. More specifically we will use the mi impute and mi estimate facilities in Stata 17 to generate and analyze the fully populated data files [21]. The number of imputed data sets will be determined by using the how many imputations procedure [22]. MICE is a flexible tool that allows imputing values for outcomes with a range of distributions (e.g., continuous, dichotomous, count, etc.). MICE assume data are missing at random (MAR) (e.g., missing is random conditional on variables in the imputation model). Variables used in the imputation models will include treatment assignment, all observed instances of the outcome being imputed, and any additional baseline variables found to significantly ( $p < .10$ ) predict subject attrition using mixed-effects logistic regression. Including baseline predictors of attrition supports the MAR assumption.

The BPI, the VAS pain severity scales (worst and average in last week), and the PHQ-9 will be administered at baseline and at all follow-up assessments. The effect of intervention on pain interference (BPI-I), pain severity, and depressive symptoms during the 3-month treatment phase will be evaluated in a generalized linear mixed model framework using the fully populated data sets generated by MICE. Models will include baseline pain and PHQ-9 depression measures as covariates. All available panel data will be included in the model to support the efficiency of estimation. Time specific estimates

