of treatment effects (e.g., the effect of treatment at 3-months) can be obtained by including the treatment by categorical (indicator variables) time interaction term. We plan to use the contrast and mimrgns post-estimation commands in Stata to recover relevant parameter estimates and test statistics. More specifically, a Wald  $\chi^2$ -test will be used to test the simple main effect of treatment at end of treatment. Additionally, we will generate graphs plotting the estimated average marginal means to facilitate substantive interpretation of results. Parallel methods will be used to evaluate the sustained effect of treatment post end-of-treatment (4-, 6-, 9-, and 12- months). Wald  $\chi^2$ -tests will again be used to test the simple main effects of treatment at post end-of-treatment assessments to determine if intervention effects are sustained over time.

The Cox proportional hazards model will be used to test the hypothesis that participants randomized to TOPPS will have higher buprenorphine treatment retention than persons randomized to HE. The outcome will be operationalized as self-reported continuous treatment since the prior interview at the time point assessed.

We will use Mplus 7 [23] to specify and estimate structural equation models (SEM) testing the hypothesis that decreased avoidance, and fear of pain mediate the relationship between intervention and pain interference and severity.

Additional baseline covariates will include ratings of pain severity, pain interference, and depression. As recommended by MacKinnon et al. [24], the statistical significance of the indirect effect will be assessed using bias-corrected bootstrapped standard errors. Significant indirect effects are consistent with the hypothesis that change in the purported mechanisms mediates the effect of intervention on outcome.

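### The primary aim covers both pain interference and pain severity, but the plan gives no success rule and does not say which severity score is primary; the error rate or the power of the primary claim is therefore undefined.

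*Combined protocol and SAP*

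**What the plan says.** Section 4.2.1 states the primary hypothesis as one sentence with two outcomes: TOPPS participants will "have less pain interference and pain severity, as measured by the BPI (Brief Pain Inventory) and a Visual Analog Scale (VAS". The time point is the close of the 3-month phase. Objective 1 (section 4.1) and hypothesis 1 (section 15.1) pair the same two outcomes. Section 4.2.3 uses the plural: "We will examine potential mediators of change in our primary outcomes". PHQ-9 depression is secondary (section 4.2.2) and is not counted here.

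Section 15.3 lists what is measured: "The BPI, the VAS pain severity scales (worst and average in last week), and the PHQ-9 will be administered at baseline". Every later visit repeats these measures. The modelling sentence is less specific: "The effect of intervention on pain interference (BPI-I), pain severity, and depressive symptoms during the 3-month treatment phase will be evaluated", using a mixed model. A Wald test "will be used to test the simple main effect of treatment at end of treatment", and a two-tailed 0.05 level "will be used for all null hypothesis tests". On covariates: "Models will include baseline pain and PHQ-9 depression measures as covariates". Table 1 in the Appendix describes the BPI as rating both severity and interference, so a BPI severity score exists as well.

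Section 15.2 plans 125 per arm, about 100 after 20% attrition, and says that 99 per arm gives 80% power for an SMD of 0.4. Section 2 reports, in the past tense, that 163 participants were randomized.

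Sections 15.1 to 15.3 contain no success rule, testing order, composite or alpha adjustment for the pain outcomes, and no other section supplies one.

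**The concern.** Interference and severity can disagree at 3 months. Section 12 tells participants that removing all pain is not the main goal and that living as they want is, so a benefit on interference without one on severity is a foreseeable result. The plan cannot say whether the primary aim would then be met. The choice, including which severity score to use, would fall to someone who knows the results.

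Each way of closing the gap has a consequence that the plan has not addressed. If any one significant pain result is enough, the chance of a false primary claim exceeds 5%. If both are needed, the chance of success is lower than the single-test power in section 15.2.

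**Working it through.** **Inputs from the documents.** SMD 0.4, 80% power, 99 per arm, 20% attrition, 125 per arm or 250 in total (15.2); two-tailed 0.05 per test (15.3); 1:1 allocation (section 5); 163 randomized (section 2), or 163/2 = 81.5 per arm, and 163 × 0.8/2 = 65.2 per arm with 20% attrition.

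**Assumed, because the documents give no values.** Correlation ρ between the outcomes' test statistics of 0.5 to 0.8; correlation b between baseline and 3-month score of 0, 0.3 or 0.5; SMD 0.4 on both outcomes for joint power.

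**1. The plan's own figure.** n = 2(1.960 + 0.842)²/0.4² = 98.1, so 99 per arm; a t-test calculation gives 99.1. This is one test at two-sided 0.05. Section 15.2 writes the level as α/2 = 0.05, but a two-sided 0.10 test would need only 78, so 0.05 two-sided is what was used. Power at 99 is 80.4%.

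**2. Any one result counts.** With k independent tests, familywise error is 1 − 0.95^k: 9.75% for two and 14.3% for three. With a common correlation ρ and c = 1.96, it is 1 − ∫φ(u)[Φ((c − √ρ·u)/√(1−ρ)) − Φ((−c − √ρ·u)/√(1−ρ))]^k du:

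| Tests | Independent | ρ = 0.5 | ρ = 0.8 |
|---|---|---|---|
| 2 | 9.75% | 9.1% | 7.8% |
| 3 | 14.3% | 12.5% | 9.8% |

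About half of each rate favours TOPPS: at ρ 0.8–0.5, 3.9–4.5% for two tests and 4.9–6.3% for three, against 2.5% for one test.

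**3. Both required (two outcomes).** Each test statistic has mean μ = 0.4·√(n/2)/√(1 − b²). Single-test power is Φ(μ − c). Joint power is ∫φ(u)[Φ((μ − c + √ρ·u)/√(1−ρ))]² du. Ranges are for ρ = 0.5 to 0.8.

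| Per arm | b | One test | Both |
|---|---|---|---|
| 99 | 0 | 80.4% | 69.2–73.3% |
| 99 | 0.3 | 83.9% | 74.2–77.7% |
| 99 | 0.5 | 90.1% | 83.5–85.8% |
| 81.5 | 0 | 72.4% | 58.6–63.8% |
| 81.5 | 0.3 | 76.3% | 63.8–68.5% |
| 81.5 | 0.5 | 83.9% | 74.1–77.7% |
| 65.2 | 0 | 62.7% | 47.0–53.0% |
| 65.2 | 0.3 | 66.8% | 51.8–57.5% |
| 65.2 | 0.5 | 75.1% | 62.1–67.0% |

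Joint power reaches 80% at 99 per arm if b is about 0.37–0.44, and at 81.5 per arm if b is about 0.54–0.58. Multiple imputation keeps all 163 in the analysis but cannot restore all the lost information, so at 20% attrition power lies between the 81.5 and 65.2 rows.

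**4. Holm across two outcomes (simulation, b = 0).** Per-outcome power with SMD 0.4 on both is 76–77% at 99 per arm, 67–68% at 81.5 and 56–57% at 65.2. If only one outcome has an effect, it is about 72%, 62% and 52%. With effects on both, Holm rejects exactly one outcome in about 9–17% of trials at 99 per arm and 10–21% at 81.5. Holm alone therefore does not settle whether the primary aim was met; the text must say what a single rejection means.

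**The case against.** **The word joining the two outcomes in 4.2.1 already requires both.** This is a natural reading, and under it the error rate is not inflated. But the plan never states it as a decision rule. A reader might infer that the trial runs an inflated primary error rate; the documents do not support that, because they do not say that one significant result is enough. What stands is that the rule is missing.

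**Then joint power is too low by design.** A reader might infer this from 69–73%. It does not follow. Section 15.3 adjusts for baseline pain and depression and uses all repeated measures, and a moderate baseline correlation brings joint power at 99 per arm to 80% or more. The defect is that the plan does not show it.

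**There are three primary tests.** This is only an inference. Section 4.2.1 refers to one VAS, and the worst and average ratings appear in the sentence on what is administered; the modelling sentence speaks of severity without a scale. Two tests is the better-supported count. The same vagueness leaves BPI severity as a candidate.

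**The lowest power figures come from recruitment.** Correct. Having 163 against 250 planned reduces even a single unadjusted test to 72% or 63%. That is a separate cause and should not be charged to multiplicity.

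**It is late to change.** Possibly. Section 2 is in the past tense, so disclosure may be the only step left.

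**Conclusion.** The concern holds as a gap in the decision rule. The plan has at least two primary pain outcomes, each tested at two-sided 0.05, an unspecified severity score, and no statement of what counts as success. That much rests on the text alone.

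The size depends on the rule that is adopted. Counting any one result puts familywise error at 7.8–9.1% for two tests or 9.8–12.5% for three, with 9.75% and 14.3% as the values under independence. Requiring both controls error, but the 80% in section 15.2 then does not describe the primary aim: at 99 per arm joint power runs from about 69% to 86%, depending on the two correlations. With 163 randomized, unadjusted joint power is 59–64% without attrition and 47–53% with 20% attrition, much of that loss being due to the smaller sample. All correlations, and an equal SMD of 0.4 on both outcomes, are assumptions.

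The trial remains analysable. The plan should be corrected because the gap bears directly on how the main result may be claimed.

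**What to change.** If unblinded outcomes have not been seen, make a dated change to the statistical plan.

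- **Severity score (4.2.1 and 15.3).** Name one: VAS worst, VAS average or BPI severity. Report the others as supportive, with 95% confidence intervals.
- **Success rule (15.3).** Choose one of:
  - (a) The primary aim is met only if interference and the named severity score are both significant at 3 months, each at two-sided 0.05. This fits the wording of 4.2.1 most closely.
  - (b) Each outcome is a separate primary claim, Holm is applied at two-sided 0.05 overall, and a single rejection supports a claim for that outcome only.
- **Power (15.2).** State that 99 per arm and 80% refer to one test. Give the power for the 163 randomized under the chosen rule, with the baseline-correlation assumption shown.

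If unblinded outcomes have been seen, a new rule would not be credible as prespecified. In that case disclose the number of primary tests and the absence of a prespecified rule, and report Holm-adjusted p-values beside the unadjusted ones.

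**Cost.** Wording only; no new data. Option (a) carries the joint power shown above. Option (b) lowers unadjusted per-outcome power from 80% to 76–77% at 99 per arm and from 72% to 67–68% with 163 and no attrition, if both outcomes have SMD 0.4; the loss is larger if only one has an effect (about 72% and 62%).

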### 4.2.2 Secondary Outcome Measures

- **Depression**

The PHQ-9 (Patient Health Questionnaire-9) will be used to measure depression severity and suicidality. It is a commonly used clinical interview that yields a depression severity score between 0 and 27.

- **Buprenorphine treatment retention**

Buprenorphine treatment retention will be measured via chart review and participant self-report.

### 4.2.3 Exploratory Outcome Measures

We will examine potential mediators of change in our primary outcomes during the 3- month treatment period, decreased avoidance of life activities (BADS [Behavioral Activation for Depression Scale]), and decreased pain anxiety or fear of pain (PASS [Pain Anxiety Symptoms Scale]).

## 5 Study Design

Eligible participants will be adult men and women currently receiving buprenorphine. Participants will be randomized to either *the TOPPS intervention* or a health education intervention (HE). We will provide both interventions over three months and follow participants for a total of 9 months in order to observe both short-term and longer-term effects of *the intervention*. Participants are recruited from two primary care, office-based addiction treatment (OBAT) buprenorphine clinics in New England: a large, university-affiliated, hospital-based clinic and a community health center's buprenorphine program. In October 2021, during the COVID-19 pandemic, recruitment was expanded to include targeted online advertisement primarily seen on social media sites, facilitated by BuildClinical LLC, a private software platform. After confirming study eligibility, the RA administers and documents informed consent within 14 days of the participant screening eligible. Prior to March of 2020, informed consent procedures

occurred in-person and took place on the same day as the participant's baseline visit. All onsite research activities were paused at the onset of COVID-19 pandemic. Remote research activities resumed in October of 2020. At that time, the study team transitioned all research activities to be conducted over the phone and via mail. Informed consent is collected via an e-consent form. Upon signing of the informed consent, a subsequent baseline interview is scheduled. Eligible participants are administered the assessment and are randomized to one of the two study arms upon completion of the interview. Randomization is stratified on three factors: study enrollment site, disability status, and currently taking an antidepressant medication using randomly permuted blocks. There is a 1:1 random allocation of the intervention between the study groups. Follow up interviews are conducted by trained RAs at 1-, 2-, 3-, 4-, 6-, 9-, and 12-months (for participants enrolled prior to October 2023) post-enrollment.

